## 2. Background and Significance

Young adults with type 1 diabetes (T1D) commonly struggle with both glycemic control and weight. The prevalence of overweight and obesity among individuals with T1D now parallels that of the general population and contributes to central obesity, dyslipidemia, elevated blood pressure, and insulin resistance, increasing risk for cardiovascular disease. There is a compelling need to develop a program of research designed to optimize not just one, but two key outcomes – glycemic control and weight status – and to address the underlying metabolic processes and behavioral challenges unique to T1D.

**Glycemic Control in Young Adults with T1D:** The benefits of intensive glucose control were demonstrated by the DCCT, with persistent benefit over 30 years later. Higher HbA1c in teens/young adults as compared to adults over age 30 was well documented in the DCCT trial. Recent T1D Exchange data demonstrate elevated HbA1c with a peak mean of over 9% in 17-year-olds, which remains elevated above 8% until a mean age of 30 years. Thus, a significant number of young adults with T1D have glucose control similar to and even worse than DCCT participants in the conventional glycemic control arm, despite advances in technology and therapeutics.

**Prevalence and Consequences of Overweight and Obesity in T1D:** Historically, people with T1D were thin or of normal weight, in part due to poor glucose control. Many participants in the DCCT intensive treatment arm experienced weight gain, which was associated with a poorer cardiometabolic profile. Now, with common use of intensive insulin therapy, and paralleling trends in the U.S. population, there is a high prevalence of overweight and obesity among people with T1D. Among young adults in the T1D Exchange Registry, 31% were overweight and 15% were obese. Longitudinal studies show that obesity increases in people with T1D as they age. Obesity is now accepted as an important contributor to long term cardiovascular risk in people with T1D.

**Determinants of Energy Balance in T1D:** Standard equations for estimating energy expenditure and dietary requirements in healthy individuals are not adequate for those with T1D. First, in patients with uncontrolled T1D, glucosuria can account for 300-400 kCal/day in obligate energy losses. Second, most studies demonstrate a modest increase in resting energy expenditure (REE; range=100-300 kCal/day) in people with T1D relative to healthy controls or predicted values. The REE increase in T1D appears to be proportionate to the degree of hyperglycemia and has been attributed to increased hepatic gluconeogenesis, driven by hyperglucagonemia. Other factors, including increased sympathetic nervous system activity, increased protein turnover and substrate transport across cellular membranes, alterations in the gut microbiome, and increases in size of metabolically active organs, may contribute to alterations in T1D energy expenditure. While exploration of these factors is beyond the scope of this proposal, there is an urgent need for a new and comprehensive assessment of the 24-hour energy requirements in people with T1D.

In addition to alterations in energy balance, T1D is characterized by impairments in metabolic flexibility, which is the ability of an organism to shift substrate oxidation rates to accommodate changes in substrate availability and is important in the development of metabolic syndrome. Compared to controls, people with T1D had

marked differences in substrate oxidation rates – with increased lipid oxidation during basal conditions – blunted ability to shift to carbohydrate oxidation during meals, and decreased thermic effect of food. Metabolic inflexibility is implicated in the development of insulin resistance in obesity and T2D, and may similarly contribute to the metabolic syndrome and increased risk of CVD in T1D.

**Weight Loss and Eating Behaviors Unique to T1D:** Successful weight loss strategies address both behavioral and psychosocial elements, grounded in established theoretical frameworks to promote behavior change, such as the Health Belief Model, Transtheoretical Model, and Theory of Reasoned Action. Self-monitoring of dietary intake and weight, use of caloric restriction, fewer calories from fat, and high levels of physical activity contribute to sustained weight loss and weight gain prevention in the general population. Conditions unique to T1D – including fear of hypoglycemia, diabulimia, or hypoglycemia-induced bingeing – may interfere with weight loss and maintenance efforts.

The process of glycemic management in T1D may interfere with achieving and maintaining healthy weight via unintended consequences of dietary restriction. Dietary restraint refers to intentional and sustained restriction of caloric intake to achieve weight loss or maintenance. T1D is described as a food culture of dietary restraint in that a strict dietary regimen characterized by carbohydrate counting drives imposed food preoccupation. Self-report measures of dietary restraint in T1D patients showed higher dietary restraint was associated with poorer glycemic control. Recurrent hypoglycemia and its associated intense hunger and permission to eat forbidden sugary foods may lead to over-eating, guilt, restriction, and possibly more episodes of hypoglycemia, creating a self-perpetuating cycle of disordered eating behavior resembling binge eating disorder and bulimia. As this restrictive-excess intake cycle repeats, individuals may increase their risk for weight gain and worsening glycemic control. Thus, models for disordered eating behaviors in T1D have expanded from insulin manipulation for weight loss to identify hypoglycemia as an important part of a cycle of dietary restraint in which hypoglycemia and its treatment can disrupt physiological hunger cues and result in a net surplus of calories with potential weight gain and worsened glycemic control.

**Dietary Approaches to Weight Loss:** According to the American Diabetes Association (ADA)'s Nutrition Therapy Recommendations, **individualization of dietary recommendations is recommended** to account for metabolic status, clinical goals, preferences, and sociocultural considerations. Optimal dietary approaches to weight management and metabolic control are highly controversial: studies (essentially all in T2D) vary in dietary approach, sample population, T2D duration and T2D treatment regimen, and importantly, in participant retention, particularly in the more restrictive dietary approaches. As reviewed by Evert et al.,(2013) weight management approaches in Look AHEAD (low fat diet) and a Mediterranean dietary pattern approach were effective in weight loss and HbA1c improvement. Both approaches incorporated relatively high carbohydrate intake (~50-55% of calories). Current ADA Standards of Medical Care emphasize that, for T2D patients, weight loss can be achieved with hypocaloric diets with macronutrient composition based on the individual patient's medical status and preferences. However, in a subset of

individuals with T2D from PREDIMED, a Mediterranean diet supplemented with either olive oil or nuts, but not explicitly calorically restricted, led to significant weight loss.

On average, people with T1D consume 45% of calories from carbohydrates, significantly less than the general US population. Further, in T1D, higher intake of carbohydrate is associated longitudinally with higher HbA1c. In T2D, a one-year hypocaloric low carbohydrate (14%) diet was effective in promoting weight loss, improving glycemic control and variability, and improving CVD risk factors. Thus it is reasonable to consider that, in T1D, a lower carbohydrate diet may be acceptable and beneficial in promoting weight loss and glycemic control. **Randomized controlled clinical trials that evaluate dietary approaches to optimize both weight management and glycemic control in T1D have not been conducted. Our proposed work will provide critically needed information to optimally design such a trial.**

**Sequential, Multiple Assignment Randomized Trial (SMART) Designs:** Sequential multiple assignment randomized trials (SMARTs) have become increasingly important tools in biomedical research because of their ability to efficiently address practical treatment comparison questions in clinically realistic settings. SMART designs address intervention decisions that unfold over time and can adapt dynamically based on patient response, as is crucial in T1D treatment. The proposed pilot SMART design will evaluate the effectiveness of experimental diets in the context of anticipated variation in patient response, both across patients and within patients over time.

### 3. Study Objectives

Our main overall objective is to develop a rigorous adaptive design to test the efficacy of a behavioral intervention to simultaneously optimize glycemic control and facilitate weight management among overweight young adults with T1D. We propose **Specific Aims** in three phases focused on young adults (age 19-30 years) with T1D. ***This protocol covers Aim 2 (Study Phase 2).***

**Aim 2, Phase 2:** Phase 2 is an initial pilot and feasibility study using a Sequential, Multiple Assignment, Randomized Trial (SMART) design to identify acceptable and effective dietary strategies to optimize both glycemic control and weight management in young adults with T1D. This pilot trial will include 84 randomized participants (42 at UNC, 42 at Stanford) in a 10.5 month behavioral intervention, with co-primary outcomes of glycemic control (HbA1C and hypoglycemia) and weight loss. (Note: data from Aim 1 Phase 1, approved under separate IRB approval, will inform the SMART pilot. Phase 1 Study 1 will inform calorie goals. Phase 1 Study 2 will inform potential counseling strategies related to dietary response to hypoglycemia.)

**Specific objectives of SMART pilot work are as follows:**

- **To assess acceptability and adherence to three distinct, evidence-based dietary approaches designed to address weight management and glycemic control.** Behavioral counseling strategies, use of carbohydrate counting for insulin dosing, and encouragement of the participant's usual level of physical activity will be the same across the 3 diets. Diets are as follows:
  - *Diet 1:* hypocaloric, moderate low fat (30% calories from fat) weight management based on the Look AHEAD study
  - *Diet 2:* hypocaloric, low carbohydrate (15-20% calories from carbohydrate, 59-63% as total fat (<10% saturated fat, at least 37% monounsaturated fat, remaining as polyunsaturated fat)
  - *Diet 3:* advice to select a healthy Mediterranean dietary pattern with no caloric restriction
- **To generate data required to inform a fully powered SMART design by:**
  - estimating the reduction in weight and body fat for each of the three diets
  - estimating the improvement in glycemic control (HbA1c, hypoglycemia) for each of the 3 diets
  - comparing the effectiveness and acceptability of the 3 dietary approaches to concurrently optimize weight and glycemic control outcomes

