## 11. Statistical Considerations

We will primarily compare the 3-month response rates to each of the three initial diets using standard statistical comparison procedures (e.g., t-tests and ANOVA) for differences in glycemic control (HbA1c and percent time in hypoglycemia) and change

in weight. In addition, we will conduct a series of secondary, hypothesis-generating analyses using standard statistical approaches as well as more complex fixed and mixed effect regression methods such as generalized additive models and random forests for these outcomes plus body fat and fat free mass. We will compare all diet sequences (there are 12) using the same outcomes and will incorporate evaluation of measures of ingestive behaviors. After adjusting for multiple comparisons, the proposed sample size of n=84 is sufficient to ensure 60% power to detect a moderate effect size (Cohen h=0.68) and 80% to detect a large effect size (Cohen h=0.85) at a significance level of 0.10 for comparing response rates among the 3 diets. Based on data reported in Wing et al (2016) and Russell et al (2014) and other preliminary data, we estimate for the same significance level and with 80% power that we will be able to detect a difference of about 3.0kg for weight change, 1.3% for HbA1c change, and 1.3 percentage point change in percent time <70mg/dl. Here we emphasize that, by design, our primary goal for this pilot work is to inform the final efficacy design, and we have therefore not designed this pilot SMART to be fully powered for all analyses.

An advantage of SMARTs is that they allow for efficient estimation of precise (i.e., deeply tailored) diet strategies. A precise diet strategy adapts treatment to the evolving health status of each participant. We will use a regression-based approximate dynamic programming algorithm known as Q-learning to estimate the precise diet strategy that maximizes weight loss while improving suboptimal or maintaining good glycemic control over the duration of the trial. The form of this estimated optimal diet strategy will generate hypotheses about how best to choose and adapt diets to individual patients. This will require the use of SMART analysis methods for balancing competing outcomes.

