Statistical Analysis Plan

ACT1ON Phase 2 (SMART Pilot) and Phase 3 (Efficacy Trial Development)

NCT03651622

January 20th, 2022

Analytic approach: The overarching objective of this study was, in addition to comparing three dietary approaches for co-management of glycemia and weight among young adults with type 1 diabetes, to identify individual-level characteristics that might drive response to a particular diet approach. Due to the COVID-19 pandemic, we recruited n=68 instead of the planned n=72 study participants, which led to the following changes in our analytic plan:

The updated analytic plan consists of the following descriptive and modeled approaches:

- Pre-COVID diet period 1 (Randomization 1): Model outcomes using generalized linear models (PROC GLM) in SAS due to lack of repeated measures
- All data, both pre- and post-COVID: Generalized estimating equations (PROC GEE) in SAS accounting for repeated measures
- Response variables for all models: Change for each of three diet periods for each of the primary and secondary outcomes:
 - o Primary outcomes:
 - Weight (kg)
 - Hemoglobin A1c (%)
 - Percent time in clinical hypoglycemia (54-60 mg/dL)
 - o Secondary outcomes:
 - Body fat percentage
 - Percent time in target glucose range (70-180 mg/dL)

Pre-COVID, diet period 1 (Randomization 1) only:

- Descriptive analysis
 - o Change in primary and secondary outcomes for each diet period *irrespective of diet* (PROC MEANS in SAS), paired t-test for overall changes in outcomes.
 - o Examine change in primary and secondary outcomes separately for each diet assignment in each of the three diet periods (PROC MEANS in SAS, paired t-test for each diet).
- Modeled analysis (PROC GLM in SAS)
 - o Change in primary and secondary outcomes for pre-COVID diet period 1 according to randomized diet assignment, and adjusted for site, baseline level of the outcome, and gender, which was imbalanced across diet assignments at baseline. Use this model to test for differences between diets.

All data, both pre- and post-COVID:

- Descriptive analysis

- Change in primary and secondary outcomes for each diet period (i.e., each randomization) *irrespective of* diet (PROC MEANS), paired t-test for overall change in outcomes
 - Examine change in primary and secondary outcomes separately for each diet in each of the three diet (i.e., randomization) periods (PROC MEANS, paired t-test for each diet) and look at mean differences between diets (PROC MEANS).

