 - Examine change in primary and secondary outcomes separately for each site and each gender in each of the three diet (i.e., randomization) periods (PROC MEANS, paired t-test for change within each stratum per diet period).
- Modeled Analysis (PROC GEE in SAS)
- Change in primary and secondary outcomes between diet periods (i.e., randomization periods) accounting for diet assignment and adjusted for site, the baseline level of the outcome, duration (months) between each diet period given that duration varied widely during the pandemic, a COVID indicator (yes/no), diet period (1, 2, or 3), and gender.

Planned analysis: consider analytic approaches that will allow for identification of individual-level characteristics that may predict individual response to a given diet assignment.

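### The SAP models weight and glycemia only one outcome at a time, so it cannot say what share of participants on each diet did well on both, although the Protocol sets that objective and planned joint analyses for it

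*Protocol*

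**What the plan says.** **Objective.** Protocol Section 3 lists three ways in which the pilot is to inform a full SMART. Two are per-outcome: estimate the weight and body fat reduction, and the glycemic improvement, for each diet. The third is different in kind: "comparing the effectiveness and acceptability of the 3 dietary approaches to concurrently optimize weight and glycemic control outcomes".

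**Protocol analysis.** Section 11 makes the comparison of 3-month response rates primary and states its power in Cohen h, an effect size for proportions. It also plans Q-learning for the strategy that "maximizes weight loss while improving suboptimal or maintaining good glycemic control over the duration of the trial", and adds: "This will require the use of SMART analysis methods for balancing competing outcomes". Table 7.1 already combines weight, glycemia and acceptability in one rule for each participant.

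**SAP.** "The updated analytic plan consists of the following descriptive and modeled approaches". The list that follows holds descriptive means with paired t-tests, PROC GLM and PROC GEE. The dependent variables are fixed as follows: "Response variables for all models: Change for each of three diet periods for each of the primary and secondary outcomes". The test between diets in period 1 is of "Change in primary and secondary outcomes for pre-COVID diet period 1 according to randomized diet assignment", adjusted for site, baseline level and gender. There is no response rate, composite, cross-outcome correlation or competing-outcome method. The one open item reads "Planned analysis: consider analytic approaches that will allow for identification of individual-level characteristics"; it concerns predictors of response and names no joint outcome. The SAP ties its changes to recruiting 68 participants instead of 72 because of the pandemic.

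**The concern.** The per-outcome models serve the first two sub-objectives. Nothing in the SAP serves the third. Two favourable means on one diet can come from different people: some lose weight while control worsens, others improve HbA1c without losing weight. The separate analyses cannot tell this from benefit in the same people, and the SAP gives no rule for reading a diet that does well on one outcome and badly on another.

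The Protocol itself gives a reason to expect the two outcomes to diverge in some participants. Section 2 notes that in uncontrolled type 1 diabetes "glucosuria can account for 300-400 kCal/day in obligate energy losses", so weight can fall as control deteriorates.

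The pilot is meant to inform and size a later SMART. In a design with this switching rule, the share of participants who meet the criteria together drives how many are re-randomized. Separate means cannot supply that share.

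**Working it through.** **1. The plan's own figure for response rates.** Section 11 states 60% power at h = 0.68 and 80% at h = 0.85, for n = 84 at significance level 0.10 after multiplicity adjustment. The adjustment and sidedness are not given; I assume 0.10/3, two-sided, so z = 2.128.

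Power = Φ(h·√(n/2) − z), with n per diet:

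- N = 84 (28 per diet): Φ(0.68·√14 − 2.128) = 66.1%; Φ(0.85·√14 − 2.128) = 85.4%.
- N = 72 (24 per diet): Φ(0.68·√12 − 2.128) = 59.0%; Φ(0.85·√12 − 2.128) = 79.3%.

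Under this assumption the stated figures fit 72, the planned number in the SAP, and not 84. The documents should reconcile the two numbers. The present point does not depend on it.

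**2. What separate results leave open.** The documents give no response rates, so the margins are assumed. Let a = share meeting the weight criterion and b = share whose control does not worsen. The joint share lies between max(0, a + b − 1) and min(a, b).

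- a = 0.50, b = 0.65: from 0.50 + 0.65 − 1 = 0.15 to 0.50.
- a = 0.60, b = 0.70: from 0.30 to 0.60 (0.42 if independent).

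**3. A less extreme illustration.** Assume normal changes: weight mean −3%, SD 4; HbA1c mean 0, SD 0.8. Count a joint response as a loss of at least 2% with an HbA1c rise below 0.5. (The self-reported hypoglycemia part of Table 7.1 is left out here for simplicity.) The margins are fixed at Φ((−2 + 3)/4) = 59.9% and Φ(0.5/0.8) = 73.4%. Only the correlation between the two changes varies:

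| Correlation of weight change with HbA1c change | Joint response |
|---|---|
| −0.6 (weight falls as HbA1c rises) | 36.5% |
| −0.3 | 40.2% |
| 0 | 43.9% |
| +0.3 | 47.9% |
| +0.6 | 52.3% |

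The separate summaries for weight and for HbA1c are the same in every row.

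**4. What the data can support.** At N = 68 there are at most 68/3 = 22.7 participants per diet.

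- Estimation: at a joint rate of 0.439, the approximate 95% half-width is 1.96·√(0.439·0.561/22.7) = 0.20. For a difference between two diets it is √2 times that, 0.29.
- Testing: 80% power at 0.10/3 two-sided needs h = (2.128 + 0.842)/√(68/6) = 0.88. From assumed reference rates of 20%, 30% or 40%, that means detecting 62%, 73% or 81%.

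A joint proportion is therefore feasible as an estimate with an interval. As a test it could detect only very large differences.

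**The case against.** The strongest defence is that the SAP already covers the safety of the inference at group level. HbA1c and hypoglycemia are co-primary and modelled in the same way as weight, so a diet that bought weight loss with worse average control would show it. The first two sub-objectives are per-outcome, as the SAP is. Section 11 says that the pilot exists to inform the later design and is not fully powered for every analysis. The SAP's closing item could in principle house Q-learning. Finally, the 15% floor needs every participant whose control worsens to be a weight responder, and samples of this size give imprecise joint proportions.

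Most of this stands, and it limits the point to the within-person link. It does not remove it. The third sub-objective is listed separately, and a group mean in each model does not answer it. The closing item only proposes to consider methods and mentions no trade-off between outcomes. A shortfall of four participants does not explain leaving out a proportion per diet. The less extreme illustration still moves the joint share from 36.5% to 52.3% with the separate results unchanged. Imprecision is a reason to call the result an estimate; it is no reason to omit it.

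**Conclusion.** The point holds as a gap between Protocol and SAP. The Protocol sets a concurrent-benefit objective and planned analyses for it; the updated SAP lists none and gives no specific reason. Section 11 does not define response for the rate comparison, so reading it as the Table 7.1 rule is an inference from how that section uses the word elsewhere. The Q-learning commitment is explicit.

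The size is the width of what stays unknown: 15% to 50% at assumed margins of 50% and 65%, or 36.5% to 52.3% in the normal illustration for correlations from −0.6 to +0.6. All of these inputs are assumptions.

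Two stronger readings are tempting and are not supported:

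- A reader might infer that the trial never planned to look at both outcomes together. Section 11 of the Protocol shows that it did.
- A reader might infer from the glucosuria figure that calorie loss alone could produce the 3.0 kg difference that Section 11 aims to detect, and so win the comparison for a diet unnoticed. That figure describes an absolute state in uncontrolled diabetes, part of which may already be present at baseline. It is not a new, sustained and uncompensated effect of a diet. The conversion would also set a per-person maximum against a difference between arm means, and a shift that large across an arm would be expected to appear in the HbA1c model.

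**What to change.** Add to the SAP, for period 1:

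- A cross-tabulation for each diet of the Table 7.1 weight criterion (at least 2% loss, with the normal-weight exception) by the full Table 7.1 glycemic criterion (HbA1c rise of at least 0.5%, or self-reported increase in hypoglycemia), with the number missing either measure.
- The joint responder proportion (weight criterion met and control not worsened) with a confidence interval for each diet and for each difference between diets.
- The within-person correlation of weight change and HbA1c change.

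Label this as estimation, and require it before any statement that a diet benefits both outcomes concurrently. State whether the competing-outcome analysis of Protocol Section 11 is restored, or why it is dropped.

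A two-outcome regression is not a substitute. With the same covariates and complete data it leaves each diet contrast unchanged, and its joint confidence region concerns means, not whether the same people benefit.

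The cost is one table and one correlation from data already collected, with no change in conduct. Intervals will be wide: at most about 23 participants per diet, and fewer if restricted to pre-COVID data.
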